7. DISCONTINUATION OF STUDY INTERVENTION AND PARTICIPANT DISCONTINUATION/WITHDRAWAL

7.1. Discontinuation of Study Intervention

Since this is a single-dose study, this section is not applicable.

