4. STUDY DESIGN

4.1. Overall Design

This study will be a Phase 1, open-label, randomized, 2-way crossover, single dose study to estimate the relative bioavailability of PF-06291826 (tafamidis) variant 12.2 mg tafamidis free acid tablets and proposed commercial 12.2 mg tafamidis tablets administered under fasted conditions in healthy participants.

Screening evaluation will occur within 28 days prior to the first dose in Period 1. Participants will be admitted to the CRU at least 12 hours prior to dosing on Day 1 and will be required to stay in the CRU for 8 days in each period. A total of 12 participants will be enrolled. Participants withdrawn from the study may be replaced. Each period will be separated by a washout of at least 16 days between administration of study drug. On Day 1 of each period, participants will receive a single dose of one of the two tafamidis formulations according to the study schema provided in [Table 3](#). Participants are to be fasted 10 hours prior to dosing and 4 hours post-dosing. For the administration, the drug products will be administrated with 240 mL of water. Medication will be administered at approximately 8:00 AM \pm 2 hours on Day 1 of each period according to a computer-generated randomization schedule.

Participants will be randomized to receive one of the treatment sequences shown in Table 3:

Table 3. B3461102 Treatment Sequence Schema

Sequence	Period 1	Period 2
1 (n = 6)	A	B
2 (n = 6)	B	A

The study medications are listed in Table 4.

Table 4. Description of Tafamidis Treatment

Treatment	Study Medication
A	1 x Variant 12.2 mg tafamidis free acid tablet (Test)
B	1 x Proposed commercial 12.2 mg tafamidis free acid tablet (Reference)

Both variant and proposed commercial 12.2 mg tafamidis free acid tablets will be supplied by Pfizer Worldwide Research and Development.

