6.1.1. Administration

On Day 1 of each period each participant will receive either one variant (Treatment A, Test) or proposed commercial (Treatment B, Reference) tafamidis 12.2 mg tablet under fasting conditions.

Following an overnight fast of at least 10 hours, participants will receive study intervention at approximately 0800 hours (plus or minus 2 hours). Investigator site personnel will administer study intervention during each period with ambient temperature water to a total volume of approximately 240 mL. Participants will swallow the study intervention whole, and will not manipulate or chew the study intervention prior to swallowing.

In order to standardize the conditions on PK sampling days, all participants will be required to refrain from lying down (except when required for BP, pulse rate, and ECG measurements), eating, and drinking beverages other than water during the first 4 hours after dosing.

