7.1.1. ECG Changes

If a clinically significant finding is identified (including, but not limited to, changes from baseline in QTcF after enrollment), the investigator or qualified designee will determine if the participant can continue in the study and if any change in participant management is needed. This review of the ECG printed at the time of collection must be documented. Any new clinically relevant finding should be reported as an AE.

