7.2.1. Withdrawal of Consent

Participants who request to discontinue receipt of study intervention will remain in the study and must continue to be followed for protocol-specified follow-up procedures. The only exception to this is when a participant specifically withdraws consent for any further contact with them or persons previously authorized by the participant to provide this information. Participants should notify the investigator in writing of the decision to withdraw consent from future follow-up, whenever possible. The withdrawal of consent should be explained in detail in the medical records by the investigator, as to whether the withdrawal is only from

PFIZER CONFIDENTIAL

further receipt of study intervention or also from study procedures and/or posttreatment study follow-up, and entered on the appropriate CRF page. In the event that vital status (whether the participant is alive or dead) is being measured, publicly available information should be used to determine vital status only as appropriately directed in accordance with local law.

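### Does calling discontinuation of study intervention not applicable undermine a crossover in which each participant is dosed twice?

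*Protocol*

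**What the plan says.** Section 7.1 of the protocol consists of one sentence: "Since this is a single-dose study, this section is not applicable". Two subsections, on ECG changes and on COVID-19, follow under the same heading.

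Section 4.1 describes a "randomized, 2-way crossover, single dose study to estimate the relative bioavailability", and Table 3 gives the sequences as A then B, or B then A. It adds: "On Day 1 of each period, participants will receive a single dose of one of the two tafamidis formulations". On spacing it says: "Each period will be separated by a washout of at least 16 days between administration of study drug". Section 6.1.1 agrees: "On Day 1 of each period each participant will receive either one variant" or one proposed commercial tablet.

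Other sections allow for stopping between the doses:

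- Section 7.2.1: "Participants who request to discontinue receipt of study intervention will remain in the study and must continue to be followed". It also asks the investigator to record whether a withdrawal covers only further dosing or also procedures and follow-up.
- Section 7.1.1: after a clinically significant finding, "the investigator or qualified designee will determine if the participant can continue in the study".
- Section 7.2 allows withdrawal at any time and provides an early discontinuation visit.

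Section 4.1 and SAP Section 2.3 allow participants withdrawn from the study to be replaced. SAP Section 6.4.2 counts discontinuations by treatment, and SAP Section 5.3.1 stops coding PK parameters as not calculated after the day a participant discontinues.

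**The concern.** The reason given in Section 7.1 does not fit the design literally. A participant who completes the study takes two doses, so there is a second dose that can be withheld or declined. Section 7.2.1 relies on a status, stopped dosing but still in the study, that Section 7.1 says does not arise.

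Two consequences would matter if they followed:

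- **Safety.** The protocol names liver abnormalities as a potential risk and sets out a work-up in Appendix 6, and the schedule of activities marks the eligibility check as Period 1 only. With Section 7.1 set aside, a Period 1 finding might seem to have no route to the decision on the Period 2 dose.
- **Analysis.** If the line between stopping the intervention and leaving the study is unclear, it might also be unclear who contributes a single period to the mixed model and who is replaced. With 12 participants, each one counts.

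**Working it through.** **1. Number of doses.** Sections 4.1 and 6.1.1 give 2 periods × 1 dose = 2 doses per completer. The conflict between Sections 7.1 and 7.2.1 is therefore real: with one dose per period, further dosing in Section 7.2.1 can only mean the Period 2 dose.

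**2. What the label means.** Title, synopsis, Section 4.1 and SAP Section 2.3 all call this a crossover and a single dose study in the same sentence. Section 6.6 uses the label to rule out dose modification. Throughout, it means single dose per period.

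**3. What Section 7.1 switches off.** It omits a list of discontinuation rules. It does not require the Period 2 dose to be given. These provisions remain in force:

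| Section | Provision |
|---|---|
| Protocol 7.1.1 | investigator decides on continuation after a significant finding; introduced under ECG changes but worded as not limited to QTcF |
| Protocol 7.2 | withdrawal at any time; early discontinuation visit |
| Protocol 7.2.1 | stopping dosing while remaining in follow-up |
| Protocol 9.3.2 (Safety Analyses) | ongoing review of AEs, ECGs, vital signs and laboratory data |
| Protocol 10.3.1 | laboratory abnormalities that change dosing or lead to discontinuation are recorded as AEs |

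The body text between Sections 8.2 and 8.5 is redacted, including Section 8.4.3, to which the schedule refers for AE assessments. Whether a further link to the second dose exists there cannot be determined.

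**4. Who enters the model.** Protocol Section 9.2 and SAP Section 4 define the PK parameter set as participants with at least one dose and at least one parameter of interest calculated. Neither refers to discontinuation status. Someone dosed only in Period 1 has Period 1 parameters and no Period 2 parameters, whichever label applies. Under SAP Section 5.3.1 the absent Period 2 value is either not generated or coded as not calculated, and the latter is set to missing for statistical analyses. The model input is the same on both readings.

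**5. Size of the replacement question.** Inputs from Protocol Section 9.5: within-participant SD on the log scale 0.098 (AUCinf) and 0.119 (Cmax), N = 12, 90% CI, 80% coverage probability. With n1 and n2 participants per sequence and df = n1 + n2 − 2, the half-width on the log scale is

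h = t(0.95, df) × SD × √[χ²(0.80, df)/df] × √[(1/n1 + 1/n2)/2]

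and the interval is the ratio × exp(±h).

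The plan's own figure at 100%, AUC, 6 + 6, df = 10: h = 1.8125 × 0.098 × √(13.442/10) × √(1/6) = 0.0841, giving 91.94% to 108.77%, width 16.83. For Cmax, replacing 0.098 by 0.119 gives h = 0.1021, 90.30% to 110.75%, width 20.45. All 14 rows of the table reproduce this way.

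Now suppose participants stop after Period 1, are not replaced, and contribute nothing to the treatment contrast:

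| Participants with both periods | AUC width at 100% | Cmax width at 100% |
|---|---|---|
| 12 (6 + 6), as planned | 16.83 | 20.45 |
| 11 (6 + 5) | 17.97 | 21.83 |
| 10 (5 + 5) | 19.17 | 23.29 |
| 10 (6 + 4) | 19.56 | 23.78 |

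One loss widens the AUC interval by 17.97/16.83 − 1 = 6.8%; two in the same sequence widen it by 19.56/16.83 − 1 = 16.2%.

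**The case for a change.** The best case for a change is that the contradiction is plain in unredacted text and a wording correction costs little. Section 7.1 is the natural place to tie Appendix 6 and the COVID-19 subsection to the second dose, and neither mentions a later dose itself. The withdrawal reasons in Section 7.2 name neither an adverse event nor an investigator decision. Replacement is offered for those withdrawn from the study, and Section 7.2.1 keeps a participant who stops dosing in the study, so that person's eligibility for replacement is undefined.

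Much of this stands as description. The two sections do conflict, and the replacement wording does leave that case open. Less of it stands as consequence. The list in Section 7.2 is not presented as exhaustive, and Section 7.1.1 already gives the investigator a continuation decision, although its reach beyond ECG findings can be argued. The synopsis ties CRU admission to continuing to meet entry criteria and mentions the stay in each period, which weakens the reading of the Period 1 only note, though that sentence too could be read as Period 1. Redaction means a missing safeguard cannot be shown. Replacement is discretionary, so the sponsor can settle a single case without departing from the plan.

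**Conclusion.** This is a slip of wording: single dose per period was shortened to single dose, and a section was marked not applicable on that basis. Sections 7.1 and 7.2.1 must be reconciled for consistency, and the content is for the sponsor's clinical team; this note takes no position on any clinical rule. No statistical change follows. The estimand, model, analysis sets and missing-data handling are the same whichever section is read as governing.

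The remaining effect is on precision, through an optional replacement decision. One unreplaced loss adds 17.97 − 16.83 = 1.14 percentage points to the AUC interval width and 21.83 − 20.45 = 1.38 to the Cmax width. The study estimates a ratio and tests no hypothesis, so this does not cross any threshold in the plan.

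The conclusion assumes that the plan's SDs hold, that few participants stop after Period 1, and that stopping is unrelated to the person's own Test/Reference ratio. It makes no claim about the redacted safety text.

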7.1.1. ECG Changes

If a clinically significant finding is identified (including, but not limited to, changes from baseline in QTcF after enrollment), the investigator or qualified designee will determine if the participant can continue in the study and if any change in participant management is needed. This review of the ECG printed at the time of collection must be documented. Any new clinically relevant finding should be reported as an AE.

7.1.2. COVID-19

If a participant is diagnosed with COVID-19 during the study, it should be reported as an AE or SAE (as appropriate) and appropriate medical intervention should be provided.

7.2. Participant Discontinuation/Withdrawal From the Study

A participant may withdraw from the study at any time at their own request. Reasons for discontinuation from the study include the following:

- Refused further follow-up
- Lost to follow-up
- Death
- Study terminated by Sponsor

At the time of discontinuing from the study, if possible, an early discontinuation visit should be conducted. See the [SoA](#) for assessments to be collected at the time of study discontinuation and follow-up and for any further evaluations that need to be completed.

The early discontinuation visit applies only to participants who are enrolled/randomized and then are prematurely withdrawn from the study. Participants should be questioned regarding their reason for withdrawal.

If a participant withdraws from the study, they may request destruction of any remaining samples taken and not tested, and the investigator must document any such requests in the site study records and notify the sponsor accordingly.

If the participant withdraws from the study and also withdraws consent (see Section 7.2.1) for disclosure of future information, no further evaluations will be performed and no additional data will be collected. The sponsor may retain and continue to use any data collected before such withdrawal of consent.

7.2.1. Withdrawal of Consent

Participants who request to discontinue receipt of study intervention will remain in the study and must continue to be followed for protocol-specified follow-up procedures. The only exception to this is when a participant specifically withdraws consent for any further contact with them or persons previously authorized by the participant to provide this information. Participants should notify the investigator in writing of the decision to withdraw consent from future follow-up, whenever possible. The withdrawal of consent should be explained in detail in the medical records by the investigator, as to whether the withdrawal is only from

PFIZER CONFIDENTIAL

further receipt of study intervention or also from study procedures and/or posttreatment study follow-up, and entered on the appropriate CRF page. In the event that vital status (whether the participant is alive or dead) is being measured, publicly available information should be used to determine vital status only as appropriately directed in accordance with local law.

7.3. Lost to Follow-up

A participant will be considered lost to follow-up if the participant repeatedly fails to return for scheduled visits and is unable to be contacted by the study site.

The following actions must be taken if a participant fails to return to the clinic for a required study visit:

- The site must attempt to contact the participant and reschedule the missed visit as soon as possible. Counsel the participant on the importance of maintaining the assigned visit schedule and ascertain whether the participant wishes to and/or should continue in the study;
- Before a participant is deemed lost to follow-up, the investigator or designee must make every effort to regain contact with the participant (where possible, 3 telephone calls and, if necessary, a certified letter to the participant's last known mailing address or local equivalent methods). These contact attempts should be documented in the participant's medical record;
- Should the participant continue to be unreachable, the participant will be considered to have withdrawn from the study.

8. STUDY ASSESSMENTS AND PROCEDURES

8.1. Administrative and Baseline Procedures

The investigator (or an appropriate delegate at the investigator site) must obtain a signed and dated ICD before performing any study-specific procedures.

Study procedures and their timing are summarized in the [SoA](#). Protocol waivers or exemptions are not allowed.

Adherence to the study design requirements, including those specified in the [SoA](#), is essential and required for study conduct.

All screening evaluations must be completed and reviewed to confirm that potential participants meet all eligibility criteria. The investigator will maintain a screening log to record details of all participants screened and to confirm eligibility or record reasons for screening failure, as applicable.

Participants will be screened within 28 days prior to administration of the study intervention to confirm that they meet the study population criteria for the study. If the time between screening and dosing exceeds 28 days as a result of unexpected delays (eg, delayed drug shipment), then participants do not require rescreening if the laboratory results obtained prior to first dose administration meet eligibility criteria.

A participant who qualified for this protocol but did not enroll from an earlier cohort/group may be used in a subsequent cohort/group without rescreening, provided laboratory results obtained prior to the first dose administration meet eligibility criteria for this study. In addition, other clinical assessments or specimen collections, eg, retained research samples, may be used without repeat collection, as appropriate.

Every effort should be made to ensure that protocol-required tests and procedures are completed as described. However, it is anticipated that from time to time there may be circumstances outside the control of the investigator that make it unfeasible to perform the test. In these cases, the investigator must take all steps necessary to ensure the safety and well-being of the participant. When a protocol-required test cannot be performed, the investigator will document the reason for the missed test and any corrective and preventive actions that they have taken to ensure that required processes are adhered to as soon as possible. The study team must be informed of these incidents in a timely manner.

If an IV catheter is utilized for blood sample collections, ECGs and vital sign assessments (pulse rate and BP) should be collected prior to the insertion of the catheter.

For samples being collected and shipped, detailed collection, processing, storage, and shipment instructions and contact information will be provided to the investigator site prior to initiation of the study.

The total blood sampling volume for individual participants in this study is approximately 185 mL. The actual collection times of blood sampling may change. Additional blood samples may be taken for safety assessments at times specified by Pfizer, provided the total volume taken during the study does not exceed 550 mL during any period of 56 consecutive days.

To prepare for study participation, participants will be instructed on the information in the [Lifestyle Considerations](#) and [Prior and Concomitant Therapy](#) sections of the protocol.

8.2. Efficacy Assessments

Analysis of efficacy is not applicable to this study.

CCI

CCI

CCI

CCI

CCI

CCI

CCI

CCI

CCI

- CCI

8.5. Pharmacokinetics

8.5.1. Plasma for Analysis of Tafamidis

Blood samples of approximately 4 mL, to provide approximately 1.5 mL, will be collected for measurement of plasma concentrations of tafamidis as specified in the [SoA](#). Instructions for the collection and handling of biological samples will be provided in the laboratory manual or by the sponsor. The actual date and time (24-hour clock time) of each sample will be recorded.

The actual times may change, but the number of samples will remain the same. All efforts will be made to obtain the samples at the exact nominal time relative to dosing. Collection of samples up to and including 10 hours after dose administration that are obtained within 10% of the nominal time relative to dosing (eg, within 6 minutes of a 60-minute sample) will not be captured as a protocol deviation, as long as the exact time of the collection is noted on the source document and the CRF/DCT. Collection of samples more than 10 hours after dose administration that are obtained \leq 1 hour away from the nominal time relative to dosing will not be captured as a protocol deviation, as long as the exact time of the collection is noted on the source document and the CRF/DCT. This protocol deviation window does not apply to samples to be collected more than 10 hours after dose administration at outpatient/follow-up visits with visit windows.

CCI

Genetic analyses will not be performed on these plasma samples. Participant confidentiality will be maintained.

Samples collected for measurement of plasma concentrations of tafamidis will be analyzed using a validated analytical method in compliance with applicable SOPs.

[figure not shown]
The PK samples must be processed and shipped as indicated in the instructions provided to the investigator site to maintain sample integrity. Any deviations from the PK sample handling procedure (eg, sample collection and processing steps, interim storage or shipping conditions), including any actions taken, must be documented and reported to the sponsor. On a case-by-case basis, the sponsor may make a determination as to whether sample integrity has been compromised.

8.6. Genetics

8.6.1. Specified Genetics

Specified genetic analyses are not evaluated in this study.

CCI

8.7. Biomarkers

Collection of samples for biomarker research is also part of this study.

8.7.1. Specified Gene Expression (RNA) Research

Specified gene expression (RNA) research is not included in this study.

8.7.2. Specified Protein Research

Specified protein research is not included in this study.

8.7.3. Specified Metabolomic Research

Specified metabolomic research is not included in this study.

CCI

Genes and other analytes (eg, proteins, RNA, nondrug metabolites) may be studied using the
CCI [REDACTED]

8.8. Immunogenicity Assessments

Immunogenicity assessments are not included in this study.

8.9. Health Economics

Health economics/medical resource utilization and health economics parameters are not evaluated in this study.

9. STATISTICAL CONSIDERATIONS

Detailed methodology for summary and statistical analyses of the data collected in this study is outlined here and further detailed in the SAP, which will be maintained by the sponsor. The SAP may modify what is outlined in the protocol where appropriate; however, any major modifications of the primary endpoint definitions or their analyses will also be reflected in a protocol amendment.

9.1. Statistical Hypotheses

There are no statistical hypotheses for this study.

9.2. Analysis Sets

For purposes of analysis, the following analysis sets are defined:

Participant Analysis Set	Description
Enrolled	“Enrolled” means a participant’s, or their legally authorized representative’s, agreement to participate in a clinical study following completion of the informed consent process and randomization/assignment to study intervention. A participant will be considered enrolled if the informed consent is not withdrawn prior to participating in any study activity after screening. Potential participants who are screened for the purpose of determining eligibility for the study, but do not participate in the study, are not considered enrolled, unless otherwise specified by the protocol.
Full analysis set	Example: All participants randomly assigned to study intervention and who take at least 1 dose of study intervention.

Participant Analysis Set	Description
CCI [REDACTED]	[REDACTED]
PK Concentration	The PK concentration population is defined as all participants who receive at least 1 dose of tafamidis and who have at least 1 measurable concentration of tafamidis.
PK Parameter	The PK parameter population is defined as all participants who receive at least 1 dose of tafamidis and who have at least 1 of the PK parameters of interest calculated.

